6.6 Safety and Harms

In addition to adverse outcome (death and events that required respiratory, cardiovascular or renal support), additional adverse events occurring before 30 day follow up will be recorded if they:

- were life-threatening
- resulted in persistent or significant disability or incapacity
- prolonged hospitalisation

Descriptive statistics of these adverse events will be calculated and reported. The following summaries will be presented:

- Number (%) participants experiencing ≥1 AE
- Number of all AEs including repeat events
- AE by Seriousness (Life threatening, Prolongs hospitalisation, Persistent or significant disability/incapacity)

6.7 Subgroup analysis

All subgroup analysis will be performed for the adult primary analysis set only. The following subgroups will be investigated:

Site

• AUROC will be presented by site for the two newly developed prediction models/triage tools for (if the number of events at each site is sufficient).

COVID-19 confirmed

 The predictive ability of the four existing and two new triage tools, and the predictive models' performance will be assessed separately on admitted patients who had COVID-19 confirmed on the follow up form and those who didn't

DNR decision

• The predictive models' performance and the new triage tools predictive ability will be investigated separately for the subgroup that had DNR decision made on day of first attendance and those that had DNR decision made later or not at all.

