5.2 Analysis populations

Name	Participants included
Primary analysis	The adult primary analysis set includes all adults (defined as age 16 or older on the
set (adults)	date of first attendance) for which presence or absence of adverse outcome could be
	ascertained (details of the ascertainment of adverse outcome given in section 8.1.1).
Primary analysis	The child primary analysis set includes all children (defined as age 15 or younger on
set (children)	the date of first attendance) for which presence or absence of adverse outcome could

The following analysis populations will be studied in the analyses:

	be ascerta	be ascertained (details of the ascertainment of adverse outcome given in section		
	8.1.1).			
Secondary	The follow	ing analysis sets will be used in the subgroup analysis detailed in section		
analyses sets	6.7, both will be on adults only due to insufficient numbers in the child cohort:			
	1.	Cases admitted and confirmed as COVID-19 (based on follow up form)		
	2.	Cases admitted and not confirmed as COVID-19 (based on follow up		
		form)		
	3.	Do Not Resuscitate (DNR) decision made on or before day of admission		
	4.	No DNR decision made, or DNR decision made later than day of		
		admission		

6 Outline of analyses

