6.5 External validation of prediction models and new triage tools

The population will be split into a development and validation cohort if at least 400 adverse outcomes are recorded (resulting in at least 200 events in each cohort). This will provide sufficient power for the triage tools to be validated [18]. We anticipate there will be insufficient events to split the child cohort and hence this population will not be split. The cohort will be split by date across certain sites. A table of characteristics for the development and validation cohort will be presented to show how the cohorts differ.

The final logistic regression models (both the initial assessment model and full model) will be externally validated by applying the predictive model and triage tools and assessing calibration, discrimination and net benefit in order to assess reproducibility. The validation cohort will also be used to compare the newly developed triage tools against the existing triage tool that performed the best in the development cohort (based on AUROC) by comparing AUROC for these tools.

In order to assess transportability of the new triage tools into different populations or settings, future cohorts must be used to examine heterogeneity in performance across different populations and settings.

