7.3.2 Calibration statistics

Calibration (the extent to which predicted and observed risk of adverse outcome agree) of the logistic regression models will be assessed using the calibration slope (where a slope of 1 indicates perfect calibration), and the observed/expected ratio (ideal value 1). These will be presented for the whole cohort on which each model is built (i.e. for adults and for children separately), and will also be derived for the COVID-19 confirmed and DNR subgroups outlined in section 6.7. Calibration will be visualised graphically using calibration plots of observed versus predicted risk.

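### Section 6.7 assesses the new models and tools in subgroups that include their own development patients, with no optimism correction, which on average favours them over the existing tools in the COVID-19 subgroups

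*SAP*

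**What the plan says.** - **Population.** Section 6.7 opens: "All subgroup analysis will be performed for the adult primary analysis set only". Section 5.2 says "The adult primary analysis set includes all adults" whose outcome can be ascertained. Neither section mentions the validation cohort.
- **Split.** Section 6.5: "The population will be split into a development and validation cohort if at least 400 adverse outcomes are recorded". Below that count there is no validation cohort.
- **COVID-19 subgroups.** Section 6.7 assesses "The predictive ability of the four existing and two new triage tools", together with the models, in admitted adults with and without confirmed COVID-19.
- **DNR subgroups.** Section 6.7 covers the models' performance and says "the new triage tools predictive ability will be investigated separately for the subgroup that had DNR decision made on day of first attendance" and for the remaining patients. It names no existing tool here.
- **Calibration.** Section 7.3.2 says of the calibration statistics: "These will be presented for the whole cohort on which each model is built". It adds that they "will also be derived for the COVID-19 confirmed and DNR subgroups outlined in section 6.7".
- **Internal validation.** Section 7.3.4 describes ten-fold cross-validation, with statistics averaged over the folds, and a bootstrap optimism correction. Both concern the prediction models. Neither is extended to subgroups or to the integer triage tools.

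**The concern.** A model scored on the patients used to build it tends to look better than it will in new patients. The SAP recognises this for the whole cohort: 7.3.4 corrects for optimism, and 6.5 reserves its named AUROC comparison of new tools with the best existing tool for the validation cohort. Section 6.7 carries neither safeguard into the subgroups.

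This matters most in the COVID-19 subgroups, because new and existing tools are reported there side by side. The existing tools' scoring is fixed in section 8 from published sources. The new tools' predictors and weights come from the study data, and one of their thresholds is chosen to give sensitivity above 95% (6.4.1, on conversion to a triage tool). Part of any advantage seen there could be overfitting. In the DNR subgroups nothing is compared, but discrimination and calibration of the new models and tools would still be reported too favourably.

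**Working it through.** **1. Who is in the subgroups.** Setting 5.2, 6.5 and 6.7 side by side:

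| Case | Source of subgroup patients | Correction stated for subgroups |
|---|---|---|
| Fewer than 400 adverse outcomes, no split | Development patients only | None |
| 400 or more, cohort split | Development and validation patients mixed | None |

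**2. The plan's own figures.** The SAP gives no figure for optimism, so there is none to reproduce. For scale, its standard error at 150 events follows from √(0.8 × 0.2 / 150) = 0.0327, against 0.033 in the section 2 table. The AUROC difference used in section 2 to size a validation cohort is 0.90 − 0.85 = 0.05.

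**3. Size of the bias, by simulation.**
- From the SAP: LASSO logistic regression (6.4); 200 planned events (section 2); 30 candidate parameters (6.4), or 68, an approximate count of the adult full-model list in 6.3.
- Assumed, not in the SAP: 8 true predictors of equal effect, independent normal predictors, true c-statistic about 0.8, event rate 5%, penalty chosen by five-fold cross-validation.
- Existing tool: a fixed, unfitted score.
- Optimism = AUROC in the development data − AUROC in 300,000 new patients.
- Pooled bias = AUROC in development data plus an equal number of new patients − AUROC in the 300,000.

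| Development events (target) | Parameters | Own data | New patients | Optimism | Pooled bias | Fixed score |
|---|---|---|---|---|---|---|
| 200 | 30 | 0.810 | 0.791 | 0.019 | 0.011 | +0.002 |
| 200 | 68 | 0.813 | 0.790 | 0.023 | 0.010 | −0.002 |
| 400 | 68 | 0.806 | 0.793 | 0.013 | 0.008 | +0.001 |
| 1000 | 68 | 0.802 | 0.797 | 0.006 | 0.004 | −0.004 |

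The pooled figure with 200 development events corresponds to a split at the 6.5 minimum of 400 in total. The fixed score shows only simulation noise.

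**4. Against the 0.05 difference.** Without a split at 200 events: 0.019/0.05 = 38% to 0.023/0.05 = 46%. Pooled, with 200 or 400 development events: 0.008/0.05 = 16% to 0.011/0.05 = 22%.

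**5. How firm these numbers are.**
- At 200 events the optimism varied between data sets with an SD of 0.017 to 0.018, about as large as its mean.
- A run with 60,000 new patients gave 0.009 at 400 events and 0.011 at 1000. The values for larger event counts are therefore uncertain by several thousandths.
- A separate simulation with about 150 events and 55 candidates gave 0.800 − 0.769 = 0.031 (SD 0.020), and 0.792 − 0.765 = 0.027 for a refit on eight predictors. That event count is relevant: if a quarter to a third of 200 events fall in children, as section 2 suggests, adults contribute 133 to 150.
- All runs concern the whole cohort. None measured optimism within a COVID-19 or DNR subgroup, or for an integer tool shaped by clinical review.

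**The case against.** The strongest reply is that the 6.7 sentence separates adults from children, and that 7.3.2 explains its own phrase about the building cohort in the same way. On that reading the SAP is silent on development versus validation patients and does not order them to be pooled. This explains why the sentence was written. It does not change what happens if the sentence is followed, because the named set contains the development patients and nothing restricts it.

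The reply also points to safeguards. The only named comparison of new with existing tools is in the validation cohort, 6.7 specifies no test between tools, and readers will have an overall optimism estimate from 7.3.4. This stands and lowers the stakes. But the 6.5 comparison is not made by subgroup, and it does not exist at all without a split.

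Three stronger readings are tempting, and the SAP supports none of them:
- A reader might infer that the new tools must look better by construction. The bias is an average, with a spread about as large as its mean at 200 events, and it does not settle a ranking.
- A reader might infer an unequal comparison in the DNR subgroups. No existing tool is assessed there.
- A reader might infer that the COVID-19 subgroups are drawn from all adults. They are limited to admitted adults.

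It is also fair that cross-validated scores for the integer tools will not be available. Clinical members review predictors, rounding and cut-offs (6.4.1), and that judgement cannot simply be rerun in each fold.

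**Conclusion.** The point holds in this limited form. As written, 6.7 scores the new models and tools wholly or partly on their own development patients, and no correction reaches the subgroups. In the COVID-19 subgroups this tilts the side-by-side figures towards the new tools on average. In the DNR subgroups it makes their absolute discrimination and calibration optimistic, and no more than that.

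The likely size is about 0.02 in AUROC at 200 events without a split, about 0.01 when development and validation patients are pooled, and less with more events. These figures rest on the simulation assumptions listed above and are carried over from the whole cohort to the subgroups. The finding itself rests on reading the sections together and does not depend on the simulated values. It is worth correcting because the SAP already applies the needed safeguards elsewhere, and because section 2 itself says that the number of events cannot be known in advance.

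**What to change.** Amend 6.7 and 7.3.2 to state:

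- **If the cohort is split:** subgroup discrimination and calibration of the new models and tools, and of any existing tools set beside them, are reported on the same validation-cohort patients.
- **If it is not split:** subgroup performance of the models is computed from the cross-validation predictions, or with the bootstrap optimism correction applied within the subgroup. The integer tools' subgroup figures are labelled 'apparent' and are not presented as a like-for-like comparison with existing tools.

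Section 7.3.4 should add that the fold-level predictions are retained, since it now mentions only averaged statistics. No new data are needed. The costs are wider subgroup intervals when only validation patients are used, and a little more analysis work to keep and use the fold-level predictions.

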6.8 Analysis on secondary outcomes

Predictive multivariable logistic regression models will also be built for the secondary outcomes listed in section 3. The independent relationship between predictor and secondary outcome, and the performance of the existing triage tools will not be investigated on any of the secondary outcomes. The analysis on secondary outcomes will be performed for adults primary analysis set only (section 5.2).

7 Detailed statistical methods and calculations

7.1 Missing data

Cases will be excluded from analysis if we are unable to ascertain if they had adverse outcome or not (i.e. they are missing follow up form). Cases will also be excluded from analysis if more than half of the variables used to develop a prediction model are not available. If particular sites have a large amount of missing data for key variables (for example age, respiratory rate) they will be excluded from analysis. The characteristics of cases with (≥20% missing) and without (<20% missing) missing data will be compared. A threshold of 20% has been chosen for comparison as we anticipate many cases to have some missing data due to the ED setting and the observational nature of this work.

It is likely that a proportion of data for most predictor variables (especially blood results) will be missing. A likely reason is that a measurement would not be made or test performed if it was expected to be normal. If a predictor variable has more than 50% data missing it will not be included in the multivariable predictive models.

Missing data will be handled in the following ways

- In the application of existing triage tools, the recommendations for handling missing data for each tool will be followed (see sections 8.2 to 8.5 for details).
- When investigating the univariate relationship between predictor and outcome (section 6.3) missing data will be treated as missing, or where appropriate treated as normal

- For building the prognostic models missing data will be handled in three ways and the results of these three scenarios will be compared, however the primary method will be multiple imputation
 - o Use multiple imputation to impute all missing predictor values
 - Assume missing predictor data is normal (when continuous variable are categorised, or when the outcome has a 'normal' option, for example CXR) or treat as missing if a continuous variable, or if no 'normal' category (see section 10 for details of which predictors will be imputed)
 - Treat all missing predictor data as missing

7.1.1 Multiple imputation

Multiple imputation (MI) will be used to impute missing values for predictor variables in the development of the prognostic model only. At least 20 and ideally 50 multiple imputation data sets will be created using chained equations. Due to the large sample size for this study, it may be computationally intensive to have more than 20 MI data sets. The multiple imputation equation will include outcome and baseline variables with both missing and complete data (for example age, sex, presenting features) to make the missing at random assumption as plausible as possible. A list of which variable will be multiply imputed, together with the factors expected to be related and used in the imputation equations is given in section 10. The imputation model will be consistent with the prognostic model used for analysis, including the functional form of continuous variables.

7.1.2 Missing AVPU

For the multivariable analysis models AVPU will be used and GCS Total will be used to impute AVPU score where AVPU is not available. The following rules will be used:

- GCS 15 = A,
- GCS 9-14 = V,
- GCS 7-9 = P,
- GCS 3-6 = U.

7.2 Modelling non-linear prognostic effects for continuous predictors

Fractional polynomials will be considered for inclusion in the logistic regression model for continuous predictors where there is a known non-linear relationship with outcome. Fractional polynomials have been shown to give similar results to restricted cubic splines; in some situations fractional polynomials better

recover simpler non-linear trends, whereas splines better recover more complex trends [19]. Functional form will be investigated first using univariate analysis and any apparent non-linear relationships will be considered for inclusion in the LASSO model. The powers to be considered are $\{-2, -1, -0.5, 0, 0.5, 1, 2, 3\}$ as recommended by Royston and Sauerbrei [20].

7.3 Prognostic Model checking

7.3.1 Overall measures of model fit

Model fit for the logistic multivariable regression models will be investigated using the Cox-Snell R² [21] and Nagelkerke's R² [22] and the likelihood ratio statistic.

7.3.2 Calibration statistics

Calibration (the extent to which predicted and observed risk of adverse outcome agree) of the logistic regression models will be assessed using the calibration slope (where a slope of 1 indicates perfect calibration), and the observed/expected ratio (ideal value 1). These will be presented for the whole cohort on which each model is built (i.e. for adults and for children separately), and will also be derived for the COVID-19 confirmed and DNR subgroups outlined in section 6.7. Calibration will be visualised graphically using calibration plots of observed versus predicted risk.

7.3.3 Discrimination statistics

Discrimination (the extent to which predictions discriminate between patients who did and did not experience adverse outcome) will be measured using the concordance statistic (C-statistic) for each of the logistic regression models, and will be presented with 95% CI.

7.3.4 Internal validation of predictive models

Cross validation of the prediction models will be conducted using 10-sample cross validation and bootstrapping.

10 sample cross validation

Within each of the 10 cycles, the predictive model is developed in all but the one omitted group, and the model performance is estimated in the omitted group, this is repeated for each of the 10 groups, and the performance statistics (discrimination and calibration) are then averaged across the 10 groups.

Bootstrapping

The same model building steps used to develop the original model are applied to each bootstrap sample. The optimism of the model will be calculated as the difference between apparent performance of the bootstrap model in the bootstrap sample and the test performance in the original sample. This procedure will be repeated for at least 100 bootstrap samples and the average of these estimates obtained in order to obtain an optimism corrected estimate of model performance.

We will also examine model stability by investigating which predictors are selected in each of the bootstrap samples.

8 Triage tool scoring and data definitions

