1.1 Study objectives

The specific objectives outlined in the protocol after each wave of the pandemic, for the hospital (emergency department) are:

- 1. To determine the discriminant value of emergency department triage methods for predicting severe illness in patients presenting with suspected pandemic respiratory infection
- 2. To determine the discriminant value of presenting clinical characteristics and routine tests for identifying severe illness
- 3. To determine the independent predictive value of presenting clinical characteristics and routine tests for severe illness
- 4. To develop new triage methods based upon presenting clinical characteristics alone or presenting clinical characteristics, electrocardiogram (ECG), chest X-ray and routine blood test results, depending upon the data available and the predictive value of variables evaluated in objective 3

2 Sample Size

The sample size will ultimately depend upon the size and severity of the pandemic. Our pragmatic data collection methods will ensure that we maximise any opportunity to evaluate emergency department triage methods in a pandemic.

Our experience in the 2009 pandemic has shown us that pre-pandemic estimates of case hospitalisation and case fatality rates can be very misleading and that sample size estimates must take into account considerable uncertainty in these estimates. Nevertheless, we have also shown that informative findings can be generated even in a pandemic with a very low rate of adverse outcome.

Given that most cases of suspected pandemic respiratory infection (even in a severe pandemic) do not result in an adverse outcome, the key variable in determining study power is the number of cases with an adverse outcome. A single cohort including at least 150 cases with adverse outcome would allow us to estimate the c-statistic of a triage method, clinical variable or test with a standard error of 0.03 (assuming the true c-statistic was 0.8). The table below shows the standard error resulting from samples with smaller numbers of adverse outcomes.

N with adverse outcome	Standard error (assuming c-statistic was 0.8)
150	0.033
125	0.036
100	0.040
75	0.046
50	0.056

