A sample with N=150 adverse outcome would estimate the sensitivity of a dichotomised rule, variable or test with a standard error as outlined in the table below, depending on the sensitivity at the threshold used. Estimates of specificity would obviously be very precise given the anticipated low prevalence of adverse outcome.

Sensitivity	Lower limit of 95% Cl
1.00	0.98
0.95	0.90
0.90	0.84
0.85	0.78
0.80	0.73

The same cohort could be used to identify independent predictors of outcome and develop new triage methods (objectives 3 and 4). The number of variables that could be tested as independent predictors of outcome in a multivariable model and for inclusion in a triage method would depend upon the sample size. Based on the rule of thumb of needing at least 10 events for each independent regression variable in a

logistic regression, a cohort with 150 cases with adverse outcome would allow us to test up to 15 parameters [4].

These estimates assume that each triage method and predictor variable will be used and tested on the whole cohort. However, we plan to explore whether different patients require different triage methods, particularly whether a different triage method is required for children and adults. Data from the 2009 H1N1 pandemic suggest that around a quarter to a third of adverse outcomes may occur in children [5] [6]. To increase the probability that we will have at least 50 cases with adverse outcome among children we will aim to recruit a total of 200 cases with adverse outcome rather than 150.

If we assume that the prevalence of adverse outcome is the same as our 2009 cohort (1%) then we would need to collect data from 20,000 cases to identify 200 with an adverse outcome. We have therefore used this estimate in planning, although it is likely to be an overestimate of the total numbers required given the mild nature of the 2009 pandemic. A more severe pandemic would allow more precise estimates to be made with no additional costs or would allow us to reduce the total number of cases required to identify 200 with an adverse outcome.

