6.4 Development of predictive model and new triage tools

New triage methods will be developed by combining potential predictors of outcome using multivariable logistic regression with Least Absolute Shrinkage and Selection Operator (LASSO) to avoid overfitting [14].

Two new prediction models and subsequent triage scores will be developed: one based on clinical variables measured at initial assessment only (initial assessment model) and the other based on all clinical variables (including blood tests and x-rays) measured in the emergency department (full model). Both models will be built for adult and child populations separately (subject to the number of events in each population, if not enough events are observed in the child population we will not attempt to build prediction models).

Univariable screening of predictors will not be used as a basis for inclusion or exclusion into the predictive model as what matters is the association of predictors with outcome *after* adjustment for other predictors [15]. Using the LASSO begins with a full model of all potentially relevant predictors and simultaneously preforms predictor selection and penalisation during model development to avoid overfitting. This penalisation method essentially shrinks the estimated association between predictor and outcome towards the null, in order to reduce the variability of predictions when the model is used in new datasets.

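### With about 5 child events per fold, the 10-fold averaged calibration slope is unstable and can miss mild overfitting; stratify and repeat the folds and make the bootstrap estimate primary

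*SAP*

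**What the plan says.** SAP section 7.3.4 plans two internal validations. In the first, the model is developed in nine of ten groups and tested in the tenth, and "the performance statistics (discrimination and calibration) are then averaged across the 10 groups". In the second, all model-building steps are repeated in at least 100 bootstrap samples, each bootstrap model is tested in the original sample, and the average optimism is subtracted. The section does not say which result leads if the two disagree. It does not mention outcome-stratified folds, repeated splits, or folds without a usable slope.

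Section 7.3.2 measures calibration by the slope and the observed/expected ratio (both ideally 1) and by plots, for adults and children separately.

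On numbers, section 2 states that "around a quarter to a third of adverse outcomes may occur in children". With the aim of "at least 50 cases with adverse outcome among children", it continues: "we will aim to recruit a total of 200 cases with adverse outcome rather than 150". Section 6.4 adds: "Both models will be built for adult and child populations separately". That is subject to enough child events, with no number given. Section 6.5 does not split the child cohort, so internal validation is the only check on a child model.

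**The concern.** Ten folds of a cohort with 50 events hold about 5 events each. A logistic calibration slope fitted to 5 events is very variable, and its distribution has a long upper tail. It is infinite if events and non-events are fully separated on the linear predictor, and undefined if the fold has no event. The C-statistic is also undefined without an event. A plain average of ten such slopes inherits the upper tail.

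An overfitted model typically shows a slope below 1, so an upward pull weakens that signal. At stake is whether a mildly overfitted child model, which gets no split-sample validation, looks well calibrated in the cross-validation result.

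**Working it through.** **1. Events per fold (SAP section 2).**
- Planned total: 20,000 × 0.01 = 200 events.
- Children: 200 × 1/4 = 50, up to 200 × 1/3 ≈ 67; per fold 5 to 6.7.
- Adults: 200 − 67 = 133 to 200 − 50 = 150; per fold 13 to 15.
- The SAP's standard errors for the C-statistic ("assuming the true c-statistic was 0.8") are reproduced by √(0.8 × 0.2 / events): 0.033 at 150 and 0.0566 at 50 (printed 0.056). At 5 events the same formula gives √(0.16/5) = 0.18 for one fold. The mean of ten has 0.18/√10 ≈ 0.057, as for the whole cohort. Small folds alone therefore do not spoil the averaged C-statistic; undefined folds do.

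**2. Folds that cannot be estimated (unstratified).**
- 50 events: P(a given fold has none) = 0.9^50 = 0.0052; over ten folds about 10 × 0.0052 = 0.05.
- 50 events, at most one in a fold: 0.0052 + 50 × 0.1 × 0.9^49 = 0.034; at least one such fold, 1 − (1 − 0.034)^10 ≈ 0.29.
- 30 events: 10 × 0.9^30 − 45 × 0.8^30 + 120 × 0.7^30 = 0.424 − 0.056 + 0.003 ≈ 0.37 for at least one fold without an event.
- Simulation at 1% prevalence, which also meets separated folds, gives at least one inestimable fold in about 4 to 7% of splits at 50 events and nearly half at 30. Stratified folds at 50 events gave none.

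**3. Averaged slope with a fixed linear predictor** (binormal, C 0.80, 50 events, inestimable folds left out). Pooled means one slope fitted to all out-of-fold predictions.

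| True slope | Prevalence | Averaged | Pooled | Averaged ≥ 1 | Pooled ≥ 1 |
|---|---|---|---|---|---|
| 0.85 | 1% (SAP) | 0.88–0.90 | 0.85 | 17–22% | 5–8% |
| 0.85 | 5% (assumed) | 0.96–0.99 | 0.86 | 39% | 11% |
| 0.75 | 5% (assumed) | – | – | 20% | 2% |
| 0.70 | 1% (SAP) | 0.73–0.74 | – | 1–1.5% | – |

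- With true slope 1 and 5 events, a single fold has mean 1.03 to 1.06 at C 0.80, 1.06 at 0.85 and 1.10 at 0.90, with SD about 0.4.
- Averaging removes most of that noise when no fold is near separation: SD 0.136 for the mean of ten folds, against 0.123 for one fit on 50 events.
- At 150 events and true slope 0.85, averaged and pooled slopes are 0.867 and 0.857.

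**4. Full cross-validation with refitting.** Assumptions not in the SAP: 2,000 patients, about 50 events, 25 candidate predictors of which 7 are real, stratified folds. ML is unpenalised maximum likelihood. True slope is that in 200,000 new patients.

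| Model, C | True | Averaged | Pooled | Bootstrap-corrected |
|---|---|---|---|---|
| ML, 0.72 | 0.64 | 0.62 | 0.54 | 0.67 |
| ML, 0.86 | 0.74 | 0.89 (median 0.82) | 0.72 | 0.75 |
| LASSO, 0.73 | 1.05 | 1.04 | 0.88 | not run |
| LASSO, 0.87 | 1.00 | 1.14 | 0.98 | not run |

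Among LASSO fits with true slope below 0.9, the averaged slope was 1 or more in 25 of 39 (64%) at C 0.73 and in 10 of 10 at C 0.87; pooled, 13% and 30%. Over all LASSO runs the averaged slope was 1 or more in 65% and 93%, and its correlation with the run's true slope was about zero. At this size it does not tell a mildly overfitted LASSO fit from a good one.

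**5. Effect of stratifying and repeating.** With models refitted at about 50 events, outcome-stratified, repeated folds cut the root mean squared error of the averaged slope from 0.25 to 0.18 and removed most inestimable folds. In that setting the true slope was 0.79, the average 0.87 and the pooled slope 0.73.

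**The case against.** The strongest reply is that section 7.3.4 already contains the safeguard. The bootstrap tests each model in the full original sample, so for children on all 50 events, and it recovered the true unpenalised slope to within about 0.03. Calibration plots and the observed/expected ratio are also planned, and averaging over folds is a legitimate convention. This stands, and it keeps the point small. It does not settle it, because the SAP does not say which internal-validation result leads.

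Three stronger readings are tempting.

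- *That the averaged slope is typically above 1 and so hides overfitting.* Means of 1.10 (1% prevalence) and 1.37 (5%) can be produced at a true slope of 0.85, but the matching medians are 0.92 and 0.97. Such means come from a few separated folds, whose slope depends on where the optimiser stops. At C 0.80 a true slope of 0.6 never averaged to 1 or more. Refitted ML models did so in 0% (C 0.72) and 3% (C 0.86) of runs.
- *That pooling should simply replace averaging.* With refitted models at C about 0.72 to 0.73, pooled slopes were biased low (0.54 against 0.64; 0.88 against 1.05) while the average was nearly unbiased.
- *That all the models are affected.* Adult primary models are not, to any practical extent. Child models are built only if events suffice, and the SAP gives no event count for the secondary outcomes.

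**Conclusion.** A minor, conditional point that holds. If a child model is built at about 50 events, unstratified and unrepeated folds leave some splits without a usable fold slope. They also give a noisy averaged slope that tends upwards: about 0.03 to 0.05 at C 0.80 and 1% prevalence, about 0.1 at an assumed 5%, more with stronger discrimination, and little or nothing at C about 0.72. The cross-validation result can therefore miss mild overfitting. The plan as a whole does not conceal it, because the bootstrap stands beside it.

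The sizes rest on a binormal linear predictor and on the assumed cohort size, predictors and signal. The LASSO results rest on 58 to 110 runs per setting. The bootstrap was checked only for unpenalised models; that it does as well for LASSO is an assumption, supported by its testing on all events. No bias was shown in the averaged observed/expected ratio or C-statistic.

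**What to change.** In section 7.3.4:

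1. Stratify the ten folds on adverse outcome and repeat the 10-fold split (for example 10 times), averaging all performance statistics over folds and repeats.
2. State how a fold whose slope or C-statistic cannot be estimated is handled, and report how many occurred.
3. For the child model and any secondary-outcome model with few events, name the bootstrap optimism-corrected calibration slope as the primary internal-validation estimate.
4. If wanted, show the slope from pooled out-of-fold predictions alongside, as a supplement and not a replacement, because it can be biased low.

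It would also help to give, in section 6.4, the minimum number of child events for building a model. The cost is a few lines of SAP text and negligible extra computing; no data collection changes.
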